**Randomized Trial of Patient-Reported Outcome Measurement in Heart Failure Clinic
(PRO-HF Trial)**

Version 5

June 30, 2023

CLINICAL TRIAL SUMMARY

Title	Randomized Trial of Patient-Reported Outcome Measurement in Heart Failure Clinic
Study Objectives	
Primary objective is to evaluate the impact of routine assessment of patient-reported health status among outpatients with heart failure on heart failure health status one year later.
 
Secondary objectives include evaluating the following:
 
 - Changes in heart failure therapy patterns - Changes in healthcare utilization (testing, clinic visits, acute care visits) - Patient experience - Concordance between clinician and patient perception of patient health status
Study Design	
This randomized clinical trial evaluates the routine assessment of patient-reported health status, using the Kansas City Cardiomyopathy Questionnaire-12 (KCCQ-12) among adult outpatients with heart failure. Any patients being seen in the heart failure clinics are eligible for enrollment. Patients will be enrolled via secure email or telephone call. They will be randomized in a 1:1 fashion to KCCQ-12 assessment or usual care with permuted block randomization stratified by clinician. Participants randomized to KCCQ-12 assessment will complete the KCCQ-12 at every heart failure clinic visit. Their results will be available to clinicians to assist with clinical management. Health status surveys will not be integrated into clinical care for patients in the usual care arm.
 
In a subset of the total study, we will compare clinician perception of patient health status and patient experience across the two arms.

Number of Participants	Minimum of 1,200 participants will be randomized; 600 patients in sub-study
Trial Location	Stanford Hospital & Clinics adult heart failure clinic
Inclusion Criteria	Adult heart failure clinic visit
Exclusion Criteria	None
Intervention	Participants randomized to KCCQ assessment will complete a KCCQ-12 survey with each heart failure clinic visit. These responses will be shared with their heart failure clinician. Treating clinicians will continue to make all diagnostic and treatment decisions at their discretions.

Primary Endpoint	KCCQ-12 score at least 1 year post-randomization
Secondary Endpoints	
Treatment patterns at 12 months:
 
 • Rates of guideline-directed therapy use • Dose of guideline-directed medical therapy • Advanced heart failure therapy evaluation • Cardiovascular testing 
Healthcare resource use at 12 months:
 
 • Heart failure clinic visits (in-person and televisits) • Heart failure telephone encounters (other than visits) • Emergency department visits • Hospitalizations (heart failure and non-heart failure)
Other Outcomes of Interest in Sub-Study	
 • Clinician perception of health status • Patient experience
Assessment Schedule	
 • Baseline KCCQ-12 at time of first clinic visit • Repeat KCCQ-12 within 12-15 months post-randomization 
Sub-study:
 
 • Patient experience survey • Clinician evaluation of patient health status
Study Duration	Patients will be enrolled for 12 months. Expected follow-up will be 12-15 months post-randomization. Patients will be followed until their first clinic visit after one year. Patients without a follow-up visit within 15 months, will be contacted for final outcome ascertainment at that time.
Statistical Considerations	A sample size of 1,200 randomized participants has 95% power to detect a mean difference in KCCQ-12 of 5 between arms (72 in KCCQ arm versus 67 in usual care; SD ~24) and an 80% power to detect a mean difference in KCCQ-12 of 4 without covariate adjustment.

TABLE OF CONTENTS

1. LIST OF ABBREVIATIONS AND DEFINITONS	5
2. BACKGROUND AND RATIONALE	6
3. HYPOTHESIS	8
4. STUDY OBJECTIVES	9
5. STUDY DESIGN	10
6. STUDY PROCEDURES	13
7. TREATMENT ARMS	17
8. STUDY ASSESSMENT AND SCHEDULE	18
9. STATISTICAL CONSIDERATIONS AND ANALYSIS PLAN	19
10. DATA HANDLING AND RECORD KEEPING	23
11. DATA AND SAFETY	24
12. PROTOCOL AMENDMENTS	25
13. REFERENCES	26
14. APPENDICES	27

1. LIST OF ABBREVIATIONS AND DEFINITIONS

EHR	Electronic health record
KCCQ-12	Kansas City Cardiomyopathy Questionnaire-12
PHI	Protected health information
PRO	Patient-reported outcome
STARR	Stanford Research Repository

2. BACKGROUND AND RATIONALE

Patient-reported outcome (PRO) measures are being increasingly emphasized by quality measurement programs and healthcare payers. The Centers for Medicare & Medicaid Services now include the measurement of patient-reported health status as a quality measure. While these measures capture patient symptoms accurately and have been shown to be highly prognostic, the feasibility and impact of PRO assessment among heart failure patients is unknown. There are no prior studies evaluating the effect of collecting this data on patient experience or quality of care. This study aims to fill those gaps.

Understanding the effect of PRO assessment on patient outcomes will determine the overall utility of the data collection. Although PRO assessment is low-cost and low-risk for a given patient, a systematic collection of PRO data and reporting is costly and shifts resources away from other potentially important interventions. There is currently a large gap in the evidence whether routine assessment of heart failure PROs improves clinical care. Determining whether PRO collection improves health-related quality of life or increases the use of guideline-recommended therapies will fill this gap. This knowledge will help weigh the benefits and costs of integrating PRO collection into clinical practice. Finding that PRO assessment leads to a significant improvement in quality of life will promote broader adoption of PRO assessment in clinical care. This could lead to an important reduction in the morbidity and mortality of heart failure. Finally, the trial will provide critical preliminary data for a multicenter trial that will verify these findings in a larger, broader sample.

3. HYPOTHESIS

Routinely assessing heart failure health status during outpatient clinic visits leads to differences in treatment patterns and better health status at one year.

4. STUDY OBJECTIVES

PRIMARY AIM

The primary aim of this study is to estimate the impact on heart failure health status in 1 year among outpatients with heart failure who are randomized to routine KCCQ-12 assessment vs. usual care.

SECONDARY AIMS

The secondary aims of this trial are to compare the following outcomes at 1 year in participants randomized to KCCQ-12 or usual care:

- Rates of guideline-directed therapy use
- Dose of guideline-directed medical therapy
- Advanced heart failure therapy evaluation
- Cardiovascular testing
- Heart failure clinic visits (in-person and televisits)
- Heart failure telephone encounters (other than visits)
- Emergency department visits
- Hospitalizations (heart failure and non-heart failure)

[figure not shown]
Additional aims include comparing the following outcomes between participants randomized to KCCQ-12 or usual care:

- Patient experience
- Clinician perception of patients' heart failure health status

5. STUDY DESIGN

This randomized trial will prospectively evaluate the effectiveness of patient-reported health status assessment among patients with heart failure seen in the Stanford Heart Failure Clinic. Any adult patients with heart failure who have a clinic visit during the 6-month enrollment period will be potentially enrolled. Before the appointment, patients will be contacted via either secure email or via telephone. Patients who consent will undergo stratified permuted block randomization to routine KCCQ assessment or usual care with stratification by treating clinician. Patients randomized to KCCQ assessment will undergo KCCQ-12 assessment at each clinic visit. The results of these assessments will be available in Epic to the clinical heart failure team. Those randomized to usual care will only undergo KCCQ-12 assessment at baseline and again at the conclusion of the study. For usual care patients, the baseline KCCQ-12 will not be displayed on Epic.

5.1 Study Flow

5.2 Study Population

Patients with an outpatient visit in Stanford adult heart failure clinic.

5.3 Inclusion/Exclusion Criteria

5.3.1 Inclusion

- Clinic visit in Stanford adult heart failure clinic
 - In-person
 - Telehealth

5.3.2 Exclusion

Patients may be excluded at the discretion of their treating cardiologist if already enrolled in an alternate clinical trial. There are no other clinical exclusions.

6. STUDY PROCEDURES

6.1 Clinic Training

Before trial enrollment, all heart failure clinic staff will receive educational material regarding patient-reported health status and the KCCQ-12. These materials will summarize data regarding the survey, its interpretation, and prognostic significance. Examples of how patient-reported health status has impacted disease management in other health conditions will also be included. The information will also be presented during an interactive educational session with heart failure clinicians and clinic staff.

6.1 Screening

All patients with a clinic visit in adult heart failure are eligible for the study. Heart failure clinicians have agreed to enroll any of their patients. Select patients may be excluded due to enrollment in alternate clinical trials.

6.2 Enrollment and Enrollment

Patients with a heart failure clinic appointment during the 6-month enrollment period will be contacted regarding potential enrollment approximately one week before their visit via secure email. The email will include information regarding the study and consent. There will also be contact information for additional information. Patients who consent will be randomized to KCCQ assessment or usual care. Patients who decline enrollment will receive no further contact from the study team.

Patients without an email response (confirming or declining participation) will be contacted via postal letter approximately two weeks before their clinic visit with information about the study and the opportunity to either enroll in the trial or decline further communication. Patients who neither decline or enroll will be contacted by telephone a few days before the visit. They have the ability to consent or decline further communication during the telephone encounter. Individuals who do not respond via telephone may also be contacted via text message.

We aim to enroll at least 1,200 patients over the 6 month enrollment period. If we enroll 1,200 patients prior to 6 months, we will still complete the 6-month enrollment period with a potential enrollment exceeding 1,200 patients given the minimal-risk nature of the study and ability to provide more precise effect estimates. If the trial fails to enroll 1,200 patients by 6 months, we will discuss reducing the trial enrollment versus extending enrollment with the IRB and the National Institute of Health (the trial sponsor).

6.3 Randomization

We will randomize patients using a secure online randomization module on REDCap. Randomization will be stratified by treating clinician with a block sizes of 2 and 4. Randomization occurs automatically via the online platform after a patient consents. Following randomization, the patient either receives the usual care KCCQ survey via REDCap or notification of an upcoming KCCQ survey via MyHealth for those in the KCCQ arm.

6.4 KCCQ-12 Completion: KCCQ Assessment Arm

6.4.1 Index Visit

For the KCCQ assessment arm, the KCCQ-12 will be collected before each heart failure clinic visit (in person and tele-visit). For patients who consent online, the KCCQ-12 will be available for online completion. For patients who do not complete the survey pre-visit, the survey can be completed during check-in. Patients who did not complete their assigned KCCQ-12 survey before the visit will be able to use their personal device or an office computer to complete the survey.

For patients who are consented via telephone, patients will be given the option of completing the survey during the call or via the online site. If completed over the phone, survey responses will be entered directly into the online database without any additional paper records.

6.4.2 Follow-up Visits

Patients in the KCCQ-12 assessment arm will complete the questionnaire prior to each follow-up clinic visit. They will be automatically messaged regarding questionnaire completion via Epic MyHealth message. Those who do not complete the questionnaire in advance will be able to complete it during check-in as described above. Patients can voluntarily select to not complete the questionnaire at any time.

6.4.3 Clinician Accessibility of KCCQ-12 Data

The KCCQ-12 is either entered by patients onto MyHealth app that is linked to Epic or by a research team member during a telephone call. For patients in the KCCQ arm, the KCCQ-12 will be printed out for clinicians at the time of the visit. The KCCQ-12 results, in addition to prior results, are also available in Epic. However, clinicians will not need to access the results or use them in any way if they select not to.

6.4 KCCQ-12 Completion: Usual Care

6.4.1 Index Visit

Patients in usual care will undergo baseline assessment of KCCQ-12. This data will be used to understand the change in KCCQ-12 between arms at follow-up. The data will be captured in the same way as the KCCQ arm using a secure website, REDCap. This data will not be available on Epic.

Patients who have not completed the KCCQ-12 questionnaire before their clinic visit will receive an email to notify them to complete the questionnaire. If they have received the notification email and the questionnaire remains unanswered, the participant will receive a phone call from the study team to help them complete the KCCQ-12.

6.4.2 Follow-up Visits

Patients in the usual care are will not be assigned any KCCQ-12 surveys during the 12-month follow-up period after their first clinic visit.

6.5 KCCQ-12 Assessment at Trial Completion

This study will compare KCCQ-12 across trial arms at least one year after randomization. All patients with clinic visits between 12-15 months after their initial visit will be assigned the KCCQ-12. The data will be collected similar to the manner described above. Patients will be messaged regarding KCCQ-12 completion one week before their clinic visit. Patients who do not complete the

KCCQ-12 will be able to complete the survey in clinic during the check-in process. Patients who do not complete the survey within 15 months (either due to not having a clinic visit between 12-15 months or not completing the survey in clinic) will be contacted via telephone to complete the survey. Among patients without clinic visits, we will ask additional questions regarding their medications and other heart failure therapies.

6.6 Sub-study: Clinic Experience Surveys

Approximately 600-patient subset will also be enrolled in a sub-study. This will involve one brief survey, conducted either in-person, via telephone or online, regarding their overall experience during clinic.

The substudy participants will be selected based on the month of enrollment. Three of the six enrollment months will automatically enroll patients in the substudy. After each clinic visit during the sub-study months, participants will receive an email notification to complete their Clinic Experience Survey if they have not already completed the survey in-person. They will receive a subsequent phone call following the email if the survey remains incomplete.

6.7 Sub-study: Clinician Perception of Health Status

A related sub-study will ask clinicians regarding their perception of patient health status. All heart failure clinicians will undergo informed consent and enrollment. Clinicians who are caring for the 600-patient sample described above (section 6.6) will be asked a brief set of questions regarding their perception of their patient's health status. Each treating clinician will also be consented given their involvement in the sub-study.

6.8 Data Storage

For the KCCQ assessment arm, the KCCQ-12 responses will be stored in REDCap, a secure research database. For patient responses collected via telephone, those responses will be transcribed directly to the database. At the end of the study, all trial data will be stored on a secure hospital server (Stanford Medicine Box) that is HIPAA-compliant and approved for patient-level data including personalized health information and personally identifiable information. Patient identifiable information and personalized health information, however, will not be stored. Each patient will be given a non-identifiable study code, and all dates will be coded based on an index date.

7. TREATMENT ARMS

7.1 KCCQ Assessment

Participants randomized to KCCQ assessment will complete the KCCQ-12 each clinic visit. Their results will be made visible to their treating clinician in Epic. The treating clinicians will be able to incorporate these results in their assessment as they see fit.

7.2 Usual Care

Patients in usual care will only undergo KCCQ assessment at the start of the trial and one-year follow-up. Their results will not be made visible to their treating clinicians. Their treating clinicians can continue to assess their quality of life and health status via clinical interview, which is the current standard of care.

8. STUDY ASSESSMENTS AND SCHEDULE

8.1 Baseline Clinical Eligibility

Any patients with a clinic visit scheduled for Stanford's adult heart failure clinic will be eligible. Eligibility will be based on the clinic schedule.

8.2 Surveys

8.2.1 KCCQ-12

The KCCQ assessment is described in detail above in Section 6.4. The KCCQ-12 is shown in Appendix A.

8.2.2 Clinic Experience Survey

The clinic experience survey will be distributed to patients in the sub-study following their first heart failure clinic visit post-randomization. The survey will be emailed to patients. Patients who do not complete the survey online will be contacted via telephone. The clinic experience survey is shown in Appendix B.

8.2.3 Clinician Perception of Health Status

The clinician perception of health status survey will be completed by the treating clinician for each patient in the sub-study following their first heart failure clinic visit post-randomization. The survey will be distributed on paper but also be available online. The clinician perception of health status survey is shown in Appendix C.

8.3 Other Baseline Clinical Data

Baseline clinical values of the following will be extracted from the EHR using structured data elements:

- Demographic characteristics (age, sex, race, ZIP)
- Vital signs, average over prior 3 months
 - Systolic/diastolic blood pressure over previous 3 months
 - Heart rate over previous 3 months
 - Respiratory rate
 - Oxygen saturation
- Most recent BMI
- Comorbidities using diagnosis coding
 - Diabetes mellitus
 - Hypertension

- Hyperlipidemia
- Chronic kidney disease
- Cerebrovascular disease
- Liver disease
- Atherosclerotic cardiovascular disease
- Peripheral vascular disease
- Chronic lung disease
- Major psychiatric disease
- Cognitive dysfunction
- Smoking status
- Cancer
- Prior procedures
 - Implantable cardiac defibrillator
 - Cardiac resynchronization therapy
 - Valve repair/replacement
 - Coronary artery bypass surgery
 - Percutaneous coronary intervention
 - Right heart catheterization
- Lab Results
 - NT-Brain natriuretic peptide
 - Creatinine
 - Hemoglobin
 - Hemoglobin A1c
 - White blood count
 - Blood urea nitrogen
- Echocardiography results
 - Left ventricular ejection fraction
 - Right ventricular systolic pressure
 - Left ventricular internal diameter during diastole
 - Right ventricular systolic function, qualitative
 - Left atrial volume
 - Average E/e'
 - Mitral regurgitation, qualitative
 - Tricuspid regurgitation, qualitative
 - Tricuspid regurgitation peak velocity
 - Estimated right ventricular systolic pressure
 - Left ventricle posterior wall thickness
 - Left ventricle septal thickness
- Medications (specific drug and dose)
 - Beta-blocker
 - Angiotensin-converting enzyme inhibitor

- Angiotensin receptor blocker
 - Angiotensin-receptor neprilysin inhibitor
 - Sodium-glucose co-transporter 2 inhibitor
 - Mineralocorticoid antagonist
 - Long-acting nitrates
 - Hydralazine
 - Loop diuretics
 - Other diuretics
 - Digoxin
 - Statin
 - Aspirin
 - Other antiarrhythmic agents
 - Other blood pressure medications
 - NSAIDs
 - Bronchodilators
 - Inhaled steroids
 - Oral steroids
- Prior Stanford Cardiology Clinic (specific to the affiliated clinician's clinic)
 - Date of last clinic visit
 - Number of clinic visits since 2018
- Other Healthcare utilization
 - Number of total Stanford clinic visits since 2018 (tele-health and in-person)
 - Prior cardiovascular diagnostic tests
 - Electrocardiogram
 - Echocardiogram
 - Stress test
 - CT Coronary Angiogram
 - Invasive coronary angiography)
 - Number of health system ED visits since 2018
 - Heart failure related
 - Non-heart failure related
 - Number of health system hospitalizations since 2018
 - Heart failure related
 - Non-heart failure related

8.4 Endpoint Assessments

Primary and secondary endpoints will be assessed using direct assessment (KCCQ-12 assessment) or EHR structured data elements. The following will be assessed between 12-18 months post-randomization:

- KCCQ-12
- Medications, as listed above

- Procedures, as listed above in addition to the following:
 - Left ventricular assist device
 - Cardiac transplant
- Transplant or LVAD workup initiation
- Hospitalizations
 - Heart-failure
 - Non-heart failure
- ED Visits
 - Heart-failure
 - Non-heart failure
- Clinic Visits
 - Heart failure clinic (tele-visit and in-person)
 - Non heart failure
- Telephone Encounters
 - Heart failure clinic
- Referrals
 - Palliative medicine
 - Psychiatry
 - Other referrals

9. STATISTICAL CONSIDERATIONS AND ANALYSIS PLAN

9.1 Primary Analysis and Statistical Power

The primary effectiveness outcome is the difference in KCCQ-12 overall summary score after one year of follow-up. Scores will be compared using mixed effects linear regression with adjustment for baseline KCCQ-12 score and a random intercept for the treating clinician. The primary analysis will be limited to patients with follow-up scores. Baseline covariate adjustment can substantially improve the precision of the statistical estimate. This has been previously shown to improve statistical power even in randomized trials with baseline covariate balance (as modeled below in the statistical power analysis).¹⁻³ The covariate used for adjustment of the primary analysis (baseline KCCQ) has been selected due to the moderate association with follow-up health status. As a secondary analysis, we will repeat the analysis with adjustment for other baseline characteristics (age and left ventricular ejection fraction) that have also been previously shown to be associated with health status.⁴⁻⁶ As an additional secondary analysis, the unadjusted KCCQ-12 scores will be compared using a two-sample t-test.

Prior work has suggested a 6 point increase in the KCCQ represents a small improvement and 11 a moderate improvement, with a standard deviation of 24.⁷⁻⁹ However, these estimates represent a significant change for an individual. A smaller mean change across a population may be clinically meaningful. The sample size calculations are based on prior Stanford Heart Failure clinic data. Prior studies of populations with heart failure have found an average KCCQ score of approximately 67. With 1,200 patients, with 20% loss to follow-up, we estimate a 97% power to detect a difference of 6, a 90% power of a mean difference of 5 in the KCCQ-12, and 73% power for a mean difference of 4 in the KCCQ-12.

As discussed above, the statistical power should be amplified with baseline covariate adjustment. We assumed baseline KCCQ-12 would explain approximately 35% of the variance in the final KCCQ-12. With baseline adjustment, we estimate approximately 55% power for a mean difference of 3 in the KCCQ-12 and 81% power for a mean difference of 4. This was estimated by simulating trial results.

Multiple sensitivity analyses to account for missing data will be conducted. First, potential assumptions around mortality will be explored. The primary analysis assumes the collection of KCCQ-12 data is independent of mortality over a 1-year follow-up. If KCCQ-12 assessment is associated with a reduction in mortality, the primary analysis will underestimate the effect of KCCQ assessment on health status. If KCCQ-12 assessment is associated with increased mortality, it will overestimate the effect of KCCQ assessment. In a secondary analysis, a KCCQ-12 score of 0 will be used for all patients who die during follow-up. This secondary analysis will test if the primary findings are consistent after placing a negative weight on mortality. Second, sensitivity analyses will account for living patients with missing data. This is important given loss to follow-up may be differential between treatment arms. This will be addressed with two different imputation techniques. The first will predict follow-up KCCQ-12 score using observed patient characteristics (including baseline KCCQ) via multiple imputation. This assumes the data is missing at random. The second approach conservatively assumes patients with missing data have worse outcomes by using the minimum observed KCCQ-12 value in the trial. These sensitivity analyses will assess the robustness of the findings.

As secondary analyses, we will compare domain scores (physical limitation, social limitation, quality of life) and the clinical summary score across arms. For these models, we will adjust for baseline domain score and include random intercepts for the treating clinician.

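### Deaths and living non-responders are handled in separate sensitivity analyses, so on the natural reading no KCCQ-12 analysis covers every randomized patient; one combined analysis should be added.

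*Combined protocol and SAP*

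**What the plan says.** All of this is in Section 9.1 of the combined protocol and SAP.

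- **Primary analysis.** "The primary analysis will be limited to patients with follow-up scores". Patients who died and living patients who did not respond are both left out.
- **First sensitivity strand, mortality.** "a KCCQ-12 score of 0 will be used for all patients who die during follow-up". The stated purpose is to see whether the primary finding holds once mortality counts against an arm. The text does not say how living patients without a score enter this analysis.
- **Second strand, non-response.** "sensitivity analyses will account for living patients with missing data". Two methods are named: multiple imputation from observed characteristics including baseline KCCQ-12, under missing at random, and substitution of the lowest score observed in the trial. The text does not say how deaths enter these analyses.

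The same paragraph gives possible differential loss between arms as the reason for the second strand. No sentence joins the two strands.

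**The concern.** A death-as-0 analysis is meant to compare arms on a score that covers everyone, dead or alive. That works only if the dead and the living are represented in their true proportions. If every known death enters but only those survivors who answered the questionnaire, the dead take up too large a share of the analysed set, and the excess grows with survivor loss. Where loss differs by arm, the penalty for mortality differs by arm for a reason unrelated to mortality. This happens even if survivors are lost completely at random.

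Unequal loss is plausible here. The trial is not blinded (Section 11.1). One arm is asked to complete the questionnaire before every visit, while the other is not surveyed during follow-up (the two Sections 6.4.2).

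At stake is the meaning of the mortality-robustness check, and the lack of any all-randomized estimate to set beside the complete-case primary result.

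**Working it through.** **1. The plan's own figure.** The plan states: "With 1,200 patients, with 20% loss to follow-up, we estimate a 97% power to detect a difference of 6", with 90% for 5 and 73% for 4. Inputs: 1,200 patients; equal allocation ("They will be randomized in a 1:1 fashion to KCCQ-12 assessment or usual care", Clinical Trial Summary); 20% loss; and "with a standard deviation of 24". Alpha is not stated, so I assume two-sided 0.05.

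- Per arm: 600 × 0.8 = 480. SE = 24 × √(2/480) = 1.549.
- Power = Φ(difference/SE − 1.96), giving 97.2%, 89.8% and 73.3%.

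The plan's figures reproduce. The unadjusted power calculation therefore rests on 960 scored patients, but the plan does not say whether deaths fall inside the 20%.

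**2. Who is in each analysis.** Mortality is not given, so I assume 5% to 10% (60 to 120 deaths).

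| | Primary | Death-as-0 | Imputation of the living |
|---|---|---|---|
| 20% includes deaths | 960 | 1,020 to 1,080 | 1,140 to 1,080 |
| 20% of survivors only | 912 to 864 | 972 to 984 | 1,140 to 1,080 |

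None reaches 1,200.

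**3. Weight given to deaths.** Let q be mortality and m the share of survivors without a score.

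- Death share of the analysed set = q / [q + (1 − q)(1 − m)].
- Over-weighting factor = death share / q = 1 / [1 − m(1 − q)].
- Arm mean = 67 × (1 − death share).

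The value 67 comes from Section 9.1 ("Prior studies of populations with heart failure have found an average KCCQ score of approximately 67"); using it as the survivor mean in both arms is my assumption. Mortality is set equal in both arms and loss is taken as completely at random, so the true difference is 0.

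| Mortality | Survivor loss A / B | Death share A / B | Over-weighting A / B | Spurious difference A − B |
|---|---|---|---|---|
| 8% | 20% / 20% | 9.8% / 9.8% | 1.23 / 1.23 | 0 |
| 5% | 18% / 22% | 6.0% / 6.3% | 1.21 / 1.26 | 0.19 |
| 6% | 10% / 18% | 6.6% / 7.2% | 1.10 / 1.20 | 0.40 |
| 8% | 15% / 25% | 9.3% / 10.4% | 1.16 / 1.30 | 0.74 |
| 10% | 10% / 30% | 11.0% / 13.7% | 1.10 / 1.37 | 1.8 |

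The 8%, 15%/25% row in full: 0.08/(0.08 + 0.92 × 0.85) = 0.0928 and 0.08/(0.08 + 0.92 × 0.75) = 0.1039. The means are 60.78 and 60.04. The all-randomized value is 67 × 0.92 = 61.64 in both arms.

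**4. Masking.** Suppose mortality is 6% versus 7% and survivor loss 25% versus 15%. The true composite difference is 67 × 0.01 = 0.67. The death shares are 0.06/0.765 = 0.0784 and 0.07/0.8605 = 0.0813, so the analysis shows 0.20.

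**5. Effect on the test.** Null trials were simulated (3,000 per setting, 600 per arm, baseline-adjusted linear model, no clinician effect). The death-as-0 analysis rejected in 4.2% to 4.6% of trials with equal 20% loss. At 5% and 10% mortality it rejected in 6.2% and 7.7% at 15%/25% loss, and in 9.8% and 16.8% at 10%/30%. With every survivor's score known, rejection was 4.3% to 5.4% and the mean difference −0.04 to 0.02. That last result shows the target of a combined analysis; imputation itself was not simulated. At 6% mortality and 10%/18% loss the standard error is about 1.6 points, so the bias is 0.4/1.6 = 0.25 standard errors and rejection is Φ(−1.71) + Φ(−2.21) ≈ 5.7%.

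**6. Incomplete knowledge of deaths.** If only a share p of deaths is known and the other deaths are treated as missing, the death share becomes pq / [pq + (1 − q)(1 − m)]. With p = 0.9 in both arms, the 0.74 falls to 67 × (0.0945 − 0.0843) = 0.68. If p = 1 − m in each arm, the share equals q and the bias vanishes.

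**The case against.** **The plan is silent; it does not prohibit.** The restriction to patients with scores is stated for the primary analysis only. A reader might infer that the death-as-0 analysis is specified to drop living non-responders. The text does not say so, and running it on imputed data would not contradict the plan. This stands: what is shown is a gap in specification. But two analysts could follow this text and report different analyses.

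**The bias is conditional and small.** This also stands. It needs unequal survivor loss; with equal loss both arms are over-weighted alike. At modest imbalance it is below 1 point. The larger type I errors need 10% versus 30% loss, which nothing in the documents suggests.

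**Deaths may not be fully known.** A reader might infer that every death is captured. Section 8.4 does not list death among the endpoint data, and the plan gives no method of ascertainment. Step 6 shows that this can shrink or remove the bias. A combined analysis shares the limitation, since it must know who is alive.

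**Much is already planned, and survivors' health status is a coherent target.** True. Section 9.1 recognises the mortality problem and states its direction. Imputing only the living answers a legitimate question. That is a reason to keep the planned analyses, but it does not supply an all-randomized one.

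**Conclusion.** The point holds as a gap worth closing cheaply. On the natural reading of Section 9.1, no planned analysis of the primary KCCQ-12 endpoint includes every randomized patient. If the death-as-0 analysis is run on known deaths plus scored survivors, unequal survivor loss creates a spurious difference favouring the arm with less loss: about 0.2 to 0.7 points across the modest imbalances tried, against design differences of 3 to 6.

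These sizes rest on assumed mortality and arm-level loss, a survivor mean of 67, loss completely at random among survivors, and full knowledge of deaths.

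Two stronger readings are not supported. This does not show that the primary result is biased, because the primary contains no death scores. Nor does it show that no analysis of any kind covers everyone, because secondary outcomes taken from the EHR could.

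**What to change.** Keep the complete-case primary and all planned sensitivity analyses. Add one all-randomized sensitivity analysis to Section 9.1:

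- Score known deaths as 0 and multiply impute living non-responders in the same analysis.
- Fit the imputation model among survivors, by arm or with arm included. Use baseline KCCQ-12, the baseline covariates, treating clinician (the primary model has a clinician intercept) and the EHR utilization during follow-up already collected under Section 8.4.
- Analyse each completed data set with the primary model, report the result beside the primary, and base the statement on robustness to mortality on it.
- State how and up to what date deaths are ascertained, and who is in each of the existing sensitivity analyses.

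The cost is a few sentences in the SAP and a little programming, since multiple imputation is already planned. The added analysis relies on missing at random among survivors, which the plan already assumes for its imputation.
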